Table 14-18	Patients pre-treated with Deferoxamine.....	95

List of abbreviations

AE	Adverse Event
AML	Acute Myeloid Leukemia
ALT	Alanine aminotransferase/glutamic pyruvic transaminase/GPT
AST	Aspartate aminotransferase/glutamic oxaloacetic transaminase/GOT
AUClast	The AUC from time zero to the last measurable concentration sampling time (tlast) (mass x time x volume-1) after single dose
AUCtau	The AUC calculated to the end of a dosing interval (tau) at steady-state (amount x time x volume-1)
b.i.d.	bis in diem/twice a day
C2hr	Post-dose 2 hr plasma concentration
Cmax	The maximum (peak) observed plasma, blood, serum, or other body fluid drug concentration after single dose administration (mass x volume-1)
CRO	Contract Research Organization
Ctrough	Pre-dose plasma concentration
CSR	Clinical study report
DFO	Deferoxamine
DFP	Deferiprone
DS&E	Drug Safety and Epidemiology
DT	Dispersible Tablet
eCRF	Electronic Case Report/Record Form
ECG	Electrocardiogram
EOS	End Of Study
i.v.	intravenous(ly)
FAS	Full Analysis Set
FCT	Film-coated tablet
GI	Gastrointestinal
ICH	International Conference on Harmonization
ICT	Iron chelation therapy
IEC	Independent Ethics Committee
IO	Iron Overload
IPSS-R	Revised International Prognostic Scoring System
IRB	Institutional Review Board
IRT	Interactive Response Technology that includes Interactive Voice Response System and Interactive Web Response System
LC-MS/MS	Liquid Chromatography-Mass Spectrometry/Mass Spectrometry
LIC	Liver Iron Concentration
MDS	Myelodysplastic syndrome
o.d.	omnia die /once a day
NCCN	National Comprehensive Cancer Network
NOAELs	No-adverse-effect-levels
PAS	PK Anaylisis Set
p.o.	per os /by mouth/orally
PHI	Protected Health Information

[figure not shown]
PRO	Patient Reported Outcome
RAP	The Report and Analysis Plan (RAP) is a regulatory document which provides evidence of preplanned analyses
RBC	Red Blood Cell
REB	Research Ethics Board
SAE	Serious Adverse Event
SEC	Study Evaluation Completion
SOP	Standard Operating Procedure
QoL	Quality of Life
VES	Visit Evaluation Schedule

Glossary of terms

Assessment	A procedure used to generate data required by the study
Dose level	The dose of drug given to the patient (total daily or weekly etc.).
Enrollment	Point/time of patient entry into the study; the point at which informed consent must be obtained (i.e. prior to starting any of the procedures described in the protocol)
Investigational drug	The study treatment whose properties are being tested in the study; this definition is consistent with US CFR 21 Section 312.3 and is synonymous with “investigational new drug.”
Investigational treatment	Drug whose properties are being tested in the study as well as their associated placebo and active treatment controls (when applicable). This also includes approved drugs used outside of their indication/approved dosage, or that are tested in a fixed combination. Investigational treatment generally does not include other study treatments administered as concomitant background therapy required or allowed by the protocol when used in within approved indication/dosage
Medication number	A unique identifier on the label of each study treatment package which is linked to one of the treatment groups of a study
Patient Number (Patient No.)	A unique identifying number assigned to each patient who enrolls in the study
Period	A subdivision of the study timeline; divides stages into smaller functional segments such as screening, baseline, titration, washout, etc.
Personal Data	Subject information collected by the Investigator that is transferred to Novartis for the purpose of the clinical trial. This data includes subject identifier information, study information and biological samples.
Premature patient withdrawal	Point/time when the patient exits from the study prior to the planned completion of all study treatment administration and/or assessments; at this time all study treatment administration is discontinued and no further assessments are planned, except End of Treatment scheduled assessments.
Stop study participation	Point/time at which the patient came in for a final evaluation visit (study evaluation schedule) or when study treatment was discontinued whichever is later
Study treatment	Includes any drug or combination of drugs in any study arm administered to the patient (subject) as part of the required study procedures, including placebo and active drug run-ins. In specific examples, it is important to judge investigational treatment component relationship relative to a study treatment combination; study treatment in this case refers to the investigational and non-investigational treatments in combination.
Study treatment discontinuation	Point/time when patient permanently stops taking study treatment for any reason
Variable	Identifier used in the data analysis; derived directly or indirectly from data collected using specified assessments at specified timepoints
Withdrawal of consent	Withdrawal of consent from the study occurs only when a subject does not want to participate in the study any longer, and does not allow any further collection of personal data

Protocol summary:

Protocol Number	C1CL670FIC05
Title	Open-label, multicenter, single arm, phase II study assessing treatment patient preference for new deferasirox formulation (film-coated tablet) compared to the reference deferasirox dispersible tablet formulation
Brief title	Study to assess patient preference of deferasirox DT (dispersible tablet) or deferasirox FCT (film-coated tablet) in thalassemia patients.
Sponsor and Clinical Phase	Novartis Phase II
Investigation type	Drug
Study type	Interventional
Purpose and rationale	
The purpose of the present study is to:
 
 • evaluate patient’s preference of deferasirox DT or deferasirox FCT formulations in patients with transfusion-dependent thalassemia or non-transfusion-dependent thalassemia as measured by preference questionnaire at Week 48 • evaluate patient’s preference of deferasirox DT or deferasirox FCT formulations or previous iron chelation in patients with transfusion-dependent thalassemia or non- transfusion-dependent thalassemia as measured by preference questionnaire at Week 4, Week 24 and Week 28. • evaluate patient’s palatability, GI symptom and satisfaction of deferasirox DT or deferasirox FCT formulations or previous iron chelation in patients with transfusion-dependent thalassemia or non- transfusion-dependent thalassemia as measured by PRO questionnaire at Screening Visit, Week 4, Week 24, Week 28 and Week 48. • evaluate any difference of preference and other assessments between each subgroup, i.e., patients with transfusion-dependent or non-transfusion-dependent thalassemia. • evaluate the overall safety of deferasirox DT compared with deferasirox FCT formulations in patients with transfusion-dependent thalassemia or non- transfusion-dependent thalassemia as measured by frequency and severity of adverse events and changes in laboratory values of interest during deferasirox FCT (Week 25 to 48) compared with deferasirox DT (Baseline day 1 to 24) • assess compliance based on pill-count evaluate efficacy of deferasirox (both DT and FCT) in decreasing serum ferritin levels
Primary Objective	
 • To evaluate patient preference of deferasirox FCT or deferasirox DT in patient with transfusion –dependent thalassemia or non-transfusion – dependent thalassemia as measured by preference questionnaire at Week 48
Secondary Objectives	
 • To evaluate patient’s palatability, GI symptom and satisfaction of deferasirox FCT or deferasirox DT or previous iron chelation based on Patient Reported Outcomes (PRO) • To evaluate patient preference of deferasirox FCT or deferasirox DT or previous iron chelation • To evaluate the reason behind preference for deferasirox FCT versus deferasirox DT

	
 • To evaluate the effect of deferasirox FCT compared with deferasirox DT on patient compliance using pill count • To evaluate the overall safety of deferasirox FCT compared with deferasirox DT • To evaluate efficacy of deferasirox (both formulations DT and FCT) in decreasing serum ferritin levels
Study design	
This is a an open-label, multicenter, single arm, phase II study aimed at collecting data on preference for iron chelation therapy in patients with transfusion-dependent thalassemia (TDT) or non-transfusion-dependent thalassemia (NTDT) throughout a 48 week treatment period.
 
The study is divided into 2 phases:
 
 - Core Phase: 
 • Screening period (visit number 1): which last up to 4 weeks to determine the patient eligibility, followed by, • Period 1: from Baseline visit Day 1 to Week 24: 
 • TDT patients: Deferasirox DT starting at 20 mg/Kg/day to maximum dose: 40 mg/Kg/day • NTDT patients: Deferasirox DT starting at 10 mg/Kg/day to maximum dose: 20 mg/Kg/day • Period 2: from Week 25 to Week 48: 
 • TDT patients: Deferasirox FCT starting at 14 mg/Kg/day to maximum dose: 28 mg/Kg/day • NTDT patients: Deferasirox FCT starting at 7 mg/Kg/day to maximum dose: 14 mg/Kg/day - Extension Phase: 
 • Deferasirox FCT: from Week 49 until Study Evaluation Completion (SEC - visit number 777) or until at least one of the End of Study criterion is met, whichever comes first: 
 • TDT patients: Deferasirox FCT starting at 14 mg/Kg/day to maximum dose: 28 mg/Kg/day • NTDT patients: Deferasirox FCT starting at 7 mg/Kg/day to maximum dose: 14 mg/Kg/day.
Population	
Approximately 145 patients aged ≥ 2 years, male or female with transfusion-dependent thalassemia or non-transfusion-dependent thalassemia requiring chelation therapy due to iron overload will be included in this study. Patients may have been previously treated with iron chelators for at least 6 months (other than Deferasirox) or be chelation naïve. In the case of a pre-treated patient, the patient must be continuously treated by other chelators for at least 6 months.
 
The investigator or designee must ensure that only patients who meet all the following inclusion and none of the exclusion criteria are offered treatment in the study.

Key Inclusion criteria	
 • Written informed consent/assent must be provided. For pediatric patients, consent will be obtained from parent(s) or legal patient's representative. • Male and female patient aged ≥ 2 years • Deferasirox naïve patient or chelation naïve patient or treated by other chelators for at least 6 months continuously, such as: 
 • Deferiprone/ DFP

	
 • Deferoxamine /DFO • Combination (DFO + DFP) • Subject is willing to discontinue current iron chelation therapy at least 5 days prior to the day 1 and for the duration of the study • Patients with transfusion-dependent thalassemia with transfusional iron overload as shown by: 
 • a serum ferritin level of > 1000 ng/ml at screening and if available, LIC > 3 mg Fe/g dw within 6 months prior to screening • Patients with non-transfusion-dependent thalassemia with iron overload as shown by: 
 • a serum ferritin level of \geq 800 ng/ml at screening and if available, LIC \geq 5 mg Fe/g dw within 6 months prior to screening.
Key Exclusion criteria	
 • Male and female patient aged < 2 years • Creatinine clearance below the contraindication limit in the locally approved prescribing information. • Serum creatinine level > 1.5 x ULN (upper limit of normal) • AST (SGOT) / ALT (SGPT) > 5xULN, unless LIC is confirmed as >10 mg Fe/dw within 6 months prior to screening visit. • Significant proteinuria as indicated by a urinary protein/creatinine ratio > 0.5 mg/mg in a non-first void urine sample. • Patients with significant impaired gastrointestinal (GI) function or GI disease that may significantly alter the absorption of oral deferasirox (e.g. ulcerative diseases, uncontrolled nausea, vomiting, diarrhea, malabsorption syndrome, or small bowel resection). • Clinical or laboratory evidence of active Hepatitis B (HBsAg in the absence of HBsAb) or Hepatitis C (HCV Ab positive with HCV RNA positive). • Patients participating in another clinical trial or receiving an investigational drug
Investigational and reference therapy	
Deferasirox (ICL670) dispersible tablets as per label (Exjade®) Deferasirox (ICL670) film- coated tablets as per label

Efficacy assessments	
Efficacy of Deferasirox DT and FCT will be evaluated based on changes in Serum ferritin levels from Day 1 baseline

Safety assessments	
 • Safety will be monitored by assessing the following parameters: 
 • Adverse events and in particular specific gastrointestinal events, up to at least 30 days following last dose of study drug • Hematology, blood chemistry (including renal and hepatic parameters) and urinalysis • Vitals signs, • Physical examinations • Ocular examinations • Auditory examinations • Chest X-Ray • ECGs
Other assessments	
 • The study will include four Patient Reported Outcome (PRO) measurements: patient preference questionnaire, patient palatability

	
questionnaires, GI symptoms and the mSITC (modified Satisfaction with iron chelation therapy) questionnaires
 
• The compliance will be measured by pill count
Data analyses	
• The primary analysis is based on patient preference of FCT over DT at Week 48, based on preference questionnaire.• The null hypothesis is that there is no difference in the proportion of patients preferring FCT or DT at Week 48. The alternative hypothesis is that there is a difference in the proportion of patients preferring FCT or DT at Week 48.• The primary analysis will be tested based on McNemar's test and Odd's Ratio (OR) and 95% Confidence Interval (CI) will also be provided for comparing the proportions of preferences over FCT and DT.
Key words	
New formulation, deferasirox, chelation, iron overload, compliance, satisfaction, palatability, PRO, preference, safety

Amendment 1 (12-Feb-2019)

Amendment rationale

The purpose of this amendment is to provide additional clarity to the study Investigators in relation to dosing of deferasirox for patients with non-transfusion dependent thalassemia (NTDT), those patients changing therapy from deferiprone, and those patients with body weight lower than 20 kg; to provide additional guidance in relation to the ocular and auditory assessments; to revise the underlying assumptions used to calculate the sample size of the study; to clarify the inclusion criterion that relates to prior therapy; to correct inconsistencies and typos; and to update withdrawal of consent language.

At the time of this amendment, 132 patients have been enrolled in the study.

The protocol has been amended to provide clearer guidance on dose titration and delineate more clearly the maximum permitted dose of deferasirox for patients with non-transfusion dependent thalassemia. In general, these patients require lower doses of iron chelation therapy than patients with transfusion dependent thalassemia and therefore additional guidance in relation to deferasirox dosing specifically for this patient group was required. The results of the THETIS study [Taher AT et al, 2016] demonstrated that doses of up to 30 mg/kg/day of deferasirox in patients with NTDT was effective (at week 52, mean LIC \pm SD decreased significantly from 15.13 ± 10.72 mg Fe/g dw at baseline to 8.46 ± 6.25 mg Fe/g dw [absolute change from baseline, -6.68 ± 7.02 mg Fe/g dw [95% CI: $-7.91, -5.45$]; P b 0.0001]). In addition, the safety profile of deferasirox in this study was consistent with the already established one. The THETIS study based dose adjustments on Liver Iron Concentration [LIC] results. In this trial, dose adjustments are based on serum ferritin levels. The relationship between LIC and serum ferritin in patients with NTDT and the derivation of corresponding clinically relevant thresholds were established by Taher AT et al [2015] using data from the THALASSA trial. These thresholds have been implemented in this amendment.

Table 14-16, which guided Investigators on the dose of deferasirox patients who had received prior deferiprone should be initiated on, has been removed due to a lack of supporting evidence. Rather, the starting dose of deferasirox will henceforth be based on the patient's serum ferritin level, consistent with clinical practice and the dosing guidance throughout the protocol. An additional change made in Appendix 14 was the inclusion of dosing guidance for children weighing less than 20 kg.

The minimum requirements for ocular and auditory assessments in pediatric patients have been clarified based on queries raised by the participating Investigators to ensure the consistency of required safety information.

Recently, additional analyses regarding patient preference with respect to deferasirox DT and deferasirox FCT from the ECLIPSE study have been published (Taher AT et al, 2018). In the ECLIPSE study, patients only received one formulation of deferasirox (either DT or FCT). Patients were asked to complete a preference questionnaire that included all possible formulations of iron chelation therapy. The preference for the FCT formulation ranged between 41-60% of patients, the preference for DT ranged between <5 – 18% and no preference (excluding missing assessments) did not exceed 10%. Based on this recent data, the assumptions underlying the sample size of this study have been updated, resulting in a reduction in the

number of patients required to enrol in the study (25 fewer) without impacting the power of the study.

The final substantial clarification made in this amendment is to specify that all patients must be deferasirox naïve rather than Exjade naïve given the availability of generic formulations of deferasirox in many of the countries participating in the study.

As of October 22, 2018, 92 patients have been enrolled in this trial. Protocol changes: The main changes in this amendment are:

- Clarify inclusion criteria number 3, by replacing Exjade naïve patient with Deferasirox naïve patient
- Clarify requirements for ocular and auditory assessments
- Add the withdrawal of informed consent section
- Provide additional dosing guidance for patients who have been treated with deferiprone
- Provide additional dosing guidance for NTDT patients
- Update [Appendix 14.1](#): Deferasirox DT and FCT dosing table starting from a body weight of 10 kg
- Revise the sample size calculation
- Correct inconsistencies, typographical and other errors detected in the protocol
- Add [Appendix 14.3](#) Algorithm for Preference questionnaire completion

IRBs/IECs

A copy of this amended protocol will be sent to the Institutional Review Board (IRBs)/Independent Ethics Committee (IECs) and Health Authorities.

The changes described in this amended protocol require IRB/IEC approval prior to implementation.

The changes herein affect the Informed Consent. Sites are required to update and submit for approval a revised Informed Consent that takes into account the changes described in this amended protocol.

1 Background

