2.3 Rationale for dose and regimen selection

Deferasirox is available in three dosing strengths: 125, 250 and 500 mg for dispersible tablets and 90, 180 and 360 mg for film-coated tablets.

For each patient, the dose is calculated by the physician based on the patient's weight, and then rounded up or down to the nearest tablet configuration, which can result in a variance between the calculated and actual dose of up to 15%. This dosing paradigm is consistent with how deferasirox DT (Exjade[®]) has been developed with regard to safety and efficacy.

All Deferasirox naïve patient or chelation naïve patients or patients who have been treated by other chelators such as Deferiprone (DFP) / Deferoxamine (DFO) or Combination (DFO + DFP) for at least 6 months continuously, at the study entry will use a starting dose of:

- Deferasirox DT of 20 mg/kg/day in transfusion-dependent thalassemia (TDT)
- Deferasirox DT of 10 mg/kg/day in non-transfusion-dependent thalassemia (NTDT),

The equivalent FCT starting dose is:

- Deferasirox FCT of 14 mg/kg/day in transfusion-dependent thalassemia (TDT)
- Deferasirox FCT of 7 mg/kg/day in non-transfusion-dependent thalassemia (NTDT).

For patients with difficulties in swallowing Deferasirox FCT, it is allowed to crush the film-coated tablets. It should be administered by sprinkling the full dose on soft food like yogurt or apple sauce (apple puree). For further instructions, refer to the [Appendix 14](#).

Dose adjustments are permitted as follows:

- Patients receiving the DT formulation: \pm 5-10 mg/kg/day; maximum daily dose: 40 mg/kg/day for TDT patients; 20 mg/kg/day for NTDT patients
- Patients receiving the FCT formulation: \pm 3.5-7 mg/kg/day; maximum daily dose: 28 mg/kg/day for TDT patients; 14 mg/kg/day for NTDT patients.

For ICT naïve patients at study entry the dose can be adjusted after 4 weeks of study treatment and for ICT pre-treated patients, the dose should be adjusted if necessary every 3 months based on serum ferritin levels

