4.1 Description of study design

This is an open-label, multicenter, single arm, phase II study aimed at collecting data on preference for iron chelation therapy in patients with transfusion-dependent thalassemia (TDT) or non-transfusion-dependent thalassemia (NTDT) throughout a 48 week treatment period.

It is a pre-requisite for the patient to provide written consent for participation in this study. This must be in place prior to performing any study-related procedures or assessments, including those described at the screening visit (please refer to [Table 7-1](#) and [Table 7-2](#)

Patients will undergo up to 4 weeks of screening and if deemed eligible, will receive deferasirox dispersible tablet (DT) formulation for 24 weeks. At the completion of 24 weeks patients will be transitioned on Week 25 to an equivalent dose of the deferasirox film coated tablet (FCT) formulation and continue treatment until Week 48 (EOT of Core Phase).

Patients can then continue deferasirox FCT formulation as per the judgment of the investigator, through an extension phase for a maximum of 12 months from the last dose of deferasirox FCT received at the end of period 2 in the Core Phase.

If one of the end of study criterion is met at any time during the study, the patient must discontinue from the study and should complete the Study Evaluation Completion (SEC - visit number 777). Please refer to [Section 4.4](#) .

Patients must be followed up for 30 days after the last dose of study drug for safety evaluation (safety follow up visit).

- Core Phase:
 - Screening phase which lasts for a maximum of 4 weeks to determine patient eligibility followed by
 - Baseline visit (day 1)
 - Period 1: deferasirox DT as 20-40 mg/kg/day dose regimen of dispersible tablet formulation for 24 weeks followed by
 - Period 2: deferasirox FCT as 14-28 mg/kg/day dose regimen of film- coated tablet for 24 weeks.
- Extension Phase:

Deferasirox FCT as 14-28 mg/kg/day dose regimen of film-coated tablet.
- PRO Validation Sub-study:
 - Patients in Egypt and Thailand may participate in this optional sub-study [sub-study protocol will only be submitted in the participating countries]

[figure not shown]
Participation in the extension phase is optional. Please refer to [Section 4.4](#) for EOS criteria.

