6.1.1 Dosing regimen

Having completed the screening period (including the 5-day wash-out period for patients previously treated with Deferiprone/DFP or Deferoxamine/DFO), eligible patients will start the core phase and be switched on the Day 1 visit to deferasirox DT for 24 weeks followed by deferasirox FCT for 24 weeks duration. Upon completion of Week 48 (Core Phase), the patient can still be treated with deferasirox FCT for a maximum of another 48 weeks or until one of the end of study criteria defined is met, whichever comes first.

The starting dose on Baseline Day 1 would be as following:

- Deferasirox DT of 20 mg/kg/day in transfusion-dependent thalassemia (TDT)
- Deferasirox DT of 10 mg/kg/day in non- transfusion-dependent thalassemia (NTDT),

Table 6-1 Equivalent FCT starting dose at Week 25

Equivalent dose to be used	
Deferasirox DT (mg/kg/day)	Deferasirox FCT (mg/kg/day)
5	3.5
10	7
15	10.5
20	14
25	17.5
30	21

Equivalent dose to be used	
Deferasirox DT (mg/kg/day)	Deferasirox FCT (mg/kg/day)
35	24.5
40	28

All iron chelation pre-treated patients who had received treatment with deferoxamine (DFO) and deferiprone (DFP) will be initiated on deferasirox DT. The dose of deferiprone will be determined by their serum ferritin and the dose of deferoxamine by using the equivalent deferasirox DT dose (see [Appendix 14.2](#)).

Dose adjustment for better treatment effects, based on serum ferritin levels and investigator's judgment, will be allowed for ICT naïve patients after 4 weeks of study treatment and for ICT pre-treated patients every 3 months. The dose adjustments will be performed in steps of 5-10 mg/kg/day for deferasirox DT or in steps of 3.5-7 mg/kg/day for deferasirox FCT.

For each patient the daily dose is calculated by the physician based on the patient's actual body weight, and then rounded up or down to the nearest whole tablet according to the available strengths of deferasirox tablets (125 mg, 250 mg and 500 mg for the DT and 90 mg, 180 mg and 360 mg for the FCT, see [Appendix 14.1](#)).

The investigator should instruct the patient (or legal patient's representative in the case of pediatric patients) to take the study drug as prescribed. All doses planned and prescribed to the patient and all dose changes including reasons for change during the study must be recorded in the eCRF.

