7.1.2 Treatment period

The duration of core phase treatment is 48 weeks. Patient visits will occur every 2 weeks during the first month of treatment and then every 4 weeks thereafter until Visit 777 (SEC).

Having completed the screening period (including the 5-day wash out period for patients previously treated with deferiprone (DFO) or deferoxamine (DFP)), patients who are eligible will be enrolled to receive deferasirox DT during 24 weeks then switch to deferasirox FCT for 24 weeks. Daily dose is calculated by the physician based on the patient's actual body weight.

At the start of treatment, iron chelation naïve patients will receive deferasirox DT 10 mg/kg (NTDT patients) or 20 mg/kg (TDT patients) once daily then will transition to the equivalent FCT dose as outlined in the following table.

Table 7-3 Equivalent dose to be used: Deferasirox DT vs Deferasirox FCT

Equivalent dose to be used	
Deferasirox DT (mg/kg/day)	Deferasirox FCT (mg/kg/day)
5	3.5
10	7
15	10.5
20	14
25	17.5
30	21
35	24.5
40	28

All iron chelation pre-treated patients will follow the below guidance:

Patients who were taking deferoxamine (DFO), will need to take the deferasirox DT equivalent deferasirox. For deferiprone (DFP) the dose of deferasirox DT will be based on their serum ferritin. Please refer to [Table 6-2](#).

At the Week 48 visit, patients will roll over to the extension phase in the case that none of the End of Study criteria is met at that time. The patient will receive deferasirox FCT following the same dose regulations and adjustments as per the core phase.

The treatment period of the extension study is approximately 52 weeks (including treatment period (48 weeks), Study Evaluation Completion and 4 weeks Safety Follow-up visits)

For details on study design and dose adjustments, see [Section 4](#) and [Section 6.3](#).

For details of assessments, see [Table 7-1](#) and [Table 7-2](#).

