| I03b                | Subjects being treated with other chelators during the 6 months within study participation.   | EXCLUDE FROM PPS             | 4                    |
| I03c                | Subjects being treated with DFP or DFO or combination (DFP+DFO) at least 6 months continuously.   | EXCLUDE FROM PPS             | 4                    |
| I04                 | Subject is not willing to discontinue current iron chelation therapy at least 5 days prior to the first day and for the duration of the study   | EXCLUDE FROM PPS             | 4                    |
| I05                 | Patients with transfusion-dependent thalassemia (independent of underlying condition) with transfusional iron overload as shown by: a serum ferritin level of <=1000 ng/ml at screening and if available, LIC <= 3 mg Fe/g dw until 6 months prior to screening | INCLUDE IN EVERYTHING        | 0                    |

| Deviation ID | Description of Deviation   | Exclusion in Analyses | Severity code |
|---------------------|---|------------------------------|----------------------|
| I06                 | Patients with non-transfusion-dependent thalassemia with iron overload as shown by: a serum ferritin level of < 800 ng/ml at screening and if available, LIC < 5 mg Fe/g dw until 6 months prior to screening | INCLUDE IN EVERYTHING        | 0                    |
| I07a                | Date informed consent obtained from subject after screening procedures  | INCLUDE IN EVERYTHING        | 0                    |
| I07b                | Date informed consent obtained from parent(s) or legal patient's representative obtained after screening procedures   | INCLUDE IN EVERYTHING        | 0                    |
| M01                 | Use of Prohibited medication as per protocol section 6.3.2.   | EXCLUDE FROM PPS             | 4                    |
| M02                 | Any investigational drug other than the study drug  | EXCLUDE FROM PPS             | 4                    |
| S01                 | Starting dose of deferasirox DT is not compliant with Protocol table 6-2.   | EXCLUDE FROM PPS             | 4                    |
| S02                 | Starting dose of deferasirox FCT is not compliant with Protocol table 7-3.  | EXCLUDE FROM PPS             | 4                    |

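### The protocol summary gives a fixed FCT starting dose at Week 25 while the detailed sections convert each patient's DT dose, and the two differ two-fold at the stated maximum doses

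*Protocol*

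**What the plan says.** **Fixed figure at Week 25.** In the protocol summary, under Study design, Period 2 runs from Week 25 to Week 48 with "TDT patients: Deferasirox FCT starting at 14 mg/Kg/day to maximum dose: 28 mg/Kg/day" and "NTDT patients: Deferasirox FCT starting at 7 mg/Kg/day to maximum dose: 14 mg/Kg/day". Neither line refers to the DT dose the patient has reached.

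**Converted dose at Week 25.** Section 4.1 has patients "transitioned on Week 25 to an equivalent dose of the deferasirox film coated tablet" formulation. Section 6.1.1 supplies Table 6-1, titled "Equivalent FCT starting dose at Week 25", which maps eight DT doses (5 to 40 mg/kg/day) to eight FCT doses (3.5 to 28 mg/kg/day). Section 7.1.2 repeats the mapping as Table 7-3, and SAP Section 1.1 repeats the transition to an equivalent dose.

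**Places that list 14 and 7 without settling the matter.** Section 2.3 gives these two figures as equivalent FCT starting doses, directly below DT starts of 20 (TDT) and 10 (NTDT). Table 6-2 lists them as FCT starting doses in a column headed weeks 1 to 4, and its footnote limits that column to chelation-naïve patients.

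**Extension.** The summary has "Deferasirox FCT: from Week 49 until Study Evaluation Completion" and gives the same fixed starts of 14 and 7. Section 4.1 says that patients may continue FCT, and Section 7.1.2 says: "The patient will receive deferasirox FCT following the same dose regulations and adjustments as per the core phase".

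**Analysis link.** SAP Section 5.5, Table 1, deviation S02 reads "Starting dose of deferasirox FCT is not compliant with Protocol table 7-3" and leads to exclusion from the PPS.

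**The concern.** A site that doses from the summary and a site that doses from Table 6-1 would give different FCT doses at Week 25 to any patient who is no longer on the default DT dose. The protocol expects such patients:

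- Table 6-3 ties TDT doses of DT 30 and 40 to ferritin above 1500 and above 2000 ng/ml, and eligibility sets no upper ferritin limit.
- Table 14-18 starts deferoxamine-pretreated patients anywhere from DT 5 to DT 40.
- Reductions before Week 25 are foreseen for creatinine (Section 6.2.1.2), for ferritin at target (Section 6.2.1.3) and for proteinuria (Section 6.2.1.4).

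Two things are at stake. The first is patient safety: under the fixed figure, a titrated patient would have the dose cut at the switch, and a patient reduced for toxicity would have it raised. The second is interpretation. Adverse events and laboratory changes are compared between DT (Day 1 to Week 24) and FCT (Weeks 25 to 48), and ferritin is followed monthly. A dose step that coincides with the change of formulation cannot be separated from it.

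**Working it through.** **Inputs.** Table 6-1 (identical to Table 7-3) for the conversion; the protocol summary for the fixed starts of 14 (TDT) and 7 (NTDT); Section 2.3 for the maximum DT doses of 40 (TDT) and 20 (NTDT). All doses are in mg/kg/day.

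**Step 1: reproduce the plan's conversion.** FCT ÷ DT is 3.5/5 = 0.70 in the first row, 14/20 = 0.70 in the fourth and 28/40 = 0.70 in the last. All eight rows give 0.70. The fixed figures are therefore the equivalents of one DT dose each: 14/0.70 = 20 and 7/0.70 = 10.

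**Step 2: compare the two readings at Week 25.** The ratio is the equivalent FCT dose divided by the fixed start.

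| DT dose | Equivalent FCT | TDT: ÷ 14 | NTDT: ÷ 7 |
|---|---|---|---|
| 5 | 3.5 | 0.25 | 0.50 |
| 10 | 7 | 0.50 | 1.00 |
| 15 | 10.5 | 0.75 | 1.50 |
| 20 | 14 | 1.00 | 2.00 |
| 25 | 17.5 | 1.25 | above stated maximum |
| 30 | 21 | 1.50 | above stated maximum |
| 35 | 24.5 | 1.75 | above stated maximum |
| 40 | 28 | 2.00 | above stated maximum |

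The readings agree at one of eight DT levels for TDT and at one of the four levels within the stated maximum for NTDT.

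- At the maximum DT dose: TDT 28/14 = 2.0; NTDT 14/7 = 2.0.
- Below the default dose the fixed figure is higher: TDT at DT 10, 14/7 = 2.0; TDT at DT 15, 14/10.5 = 1.33; NTDT at DT 5, 7/3.5 = 2.0.
- The widest gap, 14/3.5 = 4.0, needs a TDT patient at DT 5, the lowest row.

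**Step 3: one worked patient.** Section 6.2.1.2 calls for a DT reduction of 10 for a defined creatinine rise. A TDT patient going from DT 20 to DT 10 has an FCT equivalent of 10 × 0.70 = 7. The summary's figure is 14, which is the equivalent of the dose before the reduction.

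**Step 4: Week 49.** Patients are normally already on FCT, so no DT-to-FCT conversion applies and the table above does not carry over. The comparison is between the summary's fixed start and continuing the current FCT dose under core-phase rules. A TDT patient on FCT 28 would be at 28/14 = 2.0 times the summary's start, and an NTDT patient on FCT 14 at 14/7 = 2.0 times.

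**The case against.** The strongest reply is that the operative text gives one rule. Section 4.1, Section 6.1.1 with Table 6-1, Section 7.1.2 with Table 7-3, and SAP Section 1.1 all describe conversion, and S02 tests against Table 7-3. On this view the summary is shorthand: 14 and 7 are the equivalents of the default DT starts, as their position in Section 2.3 suggests, and each is paired with a maximum to describe a range. Section 4.1 itself gives 14–28 as the FCT regimen alongside the equivalent-dose transition. Much of this stands. It makes the milder reading plausible and the conflict easier to resolve. It does not remove the conflict, because the summary attaches its figures to Week 25 without saying that they hold only for patients on the default DT dose.

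Table 6-2 is weak evidence for a second rule. Its column heading and footnote confine it to weeks 1–4 and to chelation-naïve patients, and it does not mention Week 25. For chelation-naïve patients Section 7.1.2 states the conversion explicitly.

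Three stronger inferences are tempting, and the documents do not support them:

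- *That an equivalent-dose start is also written for Week 49.* No passage says so; the body text only continues FCT under core-phase rules.
- *That the primary analysis is compromised through S02.* The primary analysis uses the FAS (Protocol 10.4.1, SAP 2.5.1). S02 removes patients from the PPS, which SAP Section 2.5.4 calls supportive.
- *That the preference comparison is confounded.* Nothing in the documents links a dose step to stated preference. Dose adjustment is allowed throughout both periods, so the DT–FCT comparison was never meant to be at constant dose.

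**Conclusion.** The inconsistency at Week 25 is real and should be fixed. The summary's fixed start and the conversion in the detailed sections agree only at DT 20 (TDT) or DT 10 (NTDT). They differ two-fold at the stated maximum doses. For reduced patients the fixed figure is up to two-fold higher, or four-fold in the single case of a TDT patient at DT 5.

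At Week 49 there is a separate and lesser mismatch between a fixed start in the summary and continuation in the body.

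The harm is conditional on a site following the summary over the detailed sections, and the documents do not say how many patients will be off the default dose at Week 24. Where it happens, the patient has an unintended dose step at the switch and is lost from the PPS. This is an internal inconsistency that bears on safety and is more than clerical, but the detailed sections already point to one rule, so it ranks as should-fix.

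**What to change.** Reconcile the protocol summary, Section 2.3 and Table 6-2 with Section 4.1, Tables 6-1 and 7-3, and Section 7.1.2, so that one rule for the FCT dose at Week 25 and one for entry to the extension appear everywhere. If 14 and 7 are meant only as the equivalents of the default DT starts, the summary should say so. Then confirm that S02 tests the Week 25 rule as reconciled, and that SAP Section 1.1 matches. Which rule applies is for the sponsor to decide; this review takes no view.

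The cost is wording in a clarification letter or amendment. It needs no new procedures and does not affect the sample size.
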